1. OBJECTIVES

1.1. Primary Objective

The purpose of this study is to determine the utility of ultrasound elastography in evaluation of thyroid nodules. Elastography is a non-invasive method in which stiffness or strain images of soft tissues are used to characterize a nodule or mass lesions. Tissue that is more stiff is thought to have a greater risk of malignancy.

1.2. Secondary Objectives

No secondary objective.

2. BACKGROUND

2.1. Study Disease

Patients with thyroid nodules will be studied.

2.2. Study Agent/Device/Imaging procedure

Patients are not given a treatment or imaging agent. They are having a procedure - an Elastography Ultrasound (experimental) as well as a standard of care ultrasound.

2.3. Clinicaltrials.gov

This investigation does not require an Investigational New Drug application (IND).

2.4. Rationale

Thyroid nodules are extremely common, affecting nearly half of the adult population. Although extremely common, a minority, between 1.5 – 10% of thyroid nodules, are malignant. [1] Differentiation between benign and malignant nodules however, based on physical examination and ultrasound imaging is very difficult and generally is referred for invasive percutaneous biopsy or surgical excision for definitive diagnosis.

Because of the very common occurrence of thyroid nodules in the general public, there is a great need for a noninvasive means of stratifying those who are at greater risk of malignancy from those who are more likely to harbor a benign nodule for which no treatment is necessary.

Recent studies have examined elastography in thyroid nodules with findings of high sensitivity and good specificity. [2] Other investigators have looked at elastography in evaluation of other [3] [4] It is thought that lesions that are stiffer are more likely to represent malignancy or other pathology than benign or normal tissue which tend to be more softer.

Elastography is a noninvasive ultrasound technology which can evaluate the stiffness of a lesion compared to the background tissue. There are two major methods of measuring stiffness: strain imaging, and shear wave velocity measurement. In strain imaging, ultrasound maps the relative tissue deformity by extrinsic compression and provides a color map. Greater deformation with pressure corresponds to more elastic tissue and less deformation corresponds to stiffer tissue. In the second method, shear waves are sent through a given volume of tissue and the speed of the shear wave propagation is measured. Since stiffer tissues have higher shear wave velocities, this can be correlated with tissue

stiffness to provide a more quantitative measurement. Velocities can then be used to calculate Young modulus in kPa. [5]

Most shear wave elastography measurements currently available use a single point measurement; however, a new 2-D shear wave elastography measurement technique will be used in our study to measure stiffness of thyroid nodules. This will allow sampling of a larger area of a nodule instead of just one point, which may be more representative of the nodule's overall stiffness.

2.5. Preliminary results

Preliminary results show that the stiffness or elastography values of malignant nodules tend to be greater than benign thyroid nodules.

2.6. Study Design

- Single Group
- There will be one intervention arm
- The study will be open: no masking is used
- The study is not randomized

3. PARTICIPANT SELECTION AND ENROLLMENT PROCEDURES

3.1. Inclusion Criteria

- 3.1.1.** Age greater than or equal to 18 years.
- 3.1.2.** Presence of a thyroid nodule that is amenable to ultrasound guided fine needle aspiration.

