3.2. Exclusion Criteria

- 3.2.1.** Patients younger than 18
- 3.2.2.** Patients who are unable to lie supine for a biopsy.
- 3.2.3.** Pregnant patients

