4. IMAGING AGENT/DEVICE/PROCEDURE INFORMATION

4.1. Name of Study Agent/Device/Imaging Procedure

No imaging agent will be used in this study.

- The examination will consist of an ultrasound elastography assessment in which an ultrasound machine is used to evaluate elastography measurements of a thyroid nodule.
- Each patient will undergo one ultrasound elastography assessment of the thyroid prior to either fine needle aspiration or surgical resection of the thyroid nodule (invasive procedure is not part of the study)
- No radiation will be used for this examination. Ultrasound is an imaging modality that uses sound waves, not radiation in imaging.
- Ultrasound machines are FDA approved.

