5. STUDY PROCEDURES

5.1 Criteria for Removal from Study

After patient has ultrasound elastography of the thyroid nodule, they will have completed the study. If the patient cannot lie still in supine position then they will be removed from the study.

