5.2 Alternatives

Alternative is to not participate in the study and continue with planned standard of care ultrasound and/or fine needle aspiration of thyroid nodule.

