10. STATISTICAL CONSIDERATIONS

10.1. Statistical Design

This is a prospective single arm blinded study in which patients who come for biopsy or surgical resection will be analyzed with elastography prior to biopsy or surgical resection. A sample size of 10 vs 43 provide 80% power for detecting a difference of 0.84 m/sec at the significance level of 0.05 based on Wilcoxon rank sum test assuming that the sound velocity for benign (and malignant nodules) follows a Gaussian distribution). The standard deviation is 0.79 meters/second based on the observed standard deviation from our pilot data.

We propose to use Wilcoxon rank sum test for its robustness in cases where the velocity does not follow the Gaussian distribution. Even if the Gaussian assumption is true, the Wilcoxon rank sum test is almost as powerful as the parametric t-test.

Randomization

Patients are not randomized in this study.

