10.4.1. Analysis Population

Analysis population is 53 patients expected to consist of 10 cancer patients and 43 non-cancer patients.

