Appendix A: Inclusion/Exclusion Criteria Checklist

Inclusion Criteria (From IRB approved protocol)	Yes	No	Supporting Documentation*
1. Patient is \geq 18 years old at the time of the participation			
2. Presence of a thyroid nodule			
Exclusion Criteria (From IRB approved protocol)			
1. Patients younger than 18			
2. Patients who are unable to lie supine for a biopsy			
3. Pregnant Patients			

IV. Statement of Eligibility

This subject is [**eligible** / **ineligible**] for participation in the study.

Signature:	Date:
Printed Name:	

Signature:	Date:
Printed Name:	
Signature:	Date:
Printed Name:

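### Could the eligibility wording let in patients who will never have a malignant or benign label?

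*Combined protocol and SAP*

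**What the plan says.** Eligibility is written in two places. Section 3.1, item 3.1.2, requires "Presence of a thyroid nodule that is amenable to ultrasound guided fine needle aspiration". Appendix A, item 2, on the form that is signed to declare a subject eligible, requires "Presence of a thyroid nodule". Exclusion 3.2.2 removes "Patients who are unable to lie supine for a biopsy".

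The study population is also described elsewhere. Section 4.1 says that each patient has one elastography assessment "prior to either fine needle aspiration or surgical resection of the thyroid nodule", and that the invasive procedure lies outside the study. Section 10.1 says that "patients who come for biopsy or surgical resection will be analyzed with elastography prior to biopsy or surgical resection".

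On what follows the scan, Section 5.1 states: "After patient has ultrasound elastography of the thyroid nodule, they will have completed the study". Section 5.2 gives the alternative to taking part as to "continue with planned standard of care ultrasound and/or fine needle aspiration of thyroid nodule".

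On numbers, Section 10.4.1 states: "Analysis population is 53 patients expected to consist of 10 cancer patients and 43 non-cancer patients". Section 10.6 gives a sample size of 53, and Section 10.7 gives 53 as the accrual expected over 3 years. The single planned test (Section 10.4) is a two-sided Wilcoxon rank sum test at 0.05, comparing velocity in malignant and benign nodules.

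**The concern.** The primary test uses only patients whose nodule is classed as malignant or benign. A nodule that can be aspirated is not necessarily one that will be, and the checklist drops even that condition. A candidate with a nodule and no procedure in prospect would satisfy both eligibility texts, be scanned, and count as completed under Section 5.1. The and/or in Section 5.2 can be read as allowing for patients whose usual care is ultrasound alone.

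Expected accrual, sample size and analysis population are all 53, which is exactly 10 + 43. There is no visible margin and no stated rule on replacement. If 53 were a ceiling on enrolment, each such patient would take a place from the analysis, and with only 10 cancers expected the power could fall below the stated 80%.

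**Working it through.** **1. The texts side by side**

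| Place | Condition on the nodule | Procedure expected? |
|---|---|---|
| 3.1.2 | can be aspirated under ultrasound | not stated |
| Appendix A, item 2 | a nodule is present | not stated |
| 3.2.2 | none | presupposes a biopsy |
| 4.1 | none | yes, aspiration or resection, for each patient |
| 10.1 | none | yes, biopsy or resection |

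Sections 4.1 and 10.1 are current protocol text and bind the study as much as 3.1.2 does. Enrolling someone with no procedure in prospect would depart from both.

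The mismatch also does not run in one direction only. Read literally, 3.1.2 is narrower than 4.1 and 10.1 in one respect: it shuts out a resection patient whose nodule cannot be aspirated under ultrasound.

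Sections 5.1 and 5.2 add little. Section 5.1 fixes when the participant's own involvement ends. It does not stop the team collecting pathology, which Section 9.1 needs for the comparison. The and/or in Section 5.2 sits in a description of care outside the study and can equally cover a patient who has the standard ultrasound and then goes to surgery.

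**2. The plan's own power figure**

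Inputs from Sections 10.1 and 10.4: difference 0.84 m/s, SD 0.79 m/s, Gaussian data, groups of 10 and 43, two-sided 0.05.

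- Standardised difference: 0.84 / 0.79 = 1.063.
- Test: U is the rank sum of the malignant group minus n1(n1+1)/2. Under the null its mean is n1·n2/2 = 215 and its SD is √[n1·n2(n1+n2+1)/12] = √(430 × 54 / 12) = 44.0.
- Simulated power: 81.3% with the normal approximation (40,000 runs) and 81.5% with the exact test (200,000 runs).
- Cross-checks: a noncentral t calculation with efficiency 3/π gives 82.7%. Noether's formula, with P(malignant > benign) = Φ(1.063/√2) = 0.774, gives 77.1%.

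The stated 80% is sound.

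**3. What lost labels would do** (exact test, simulated)

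| Malignant / benign | Power |
|---|---|
| 10 / 43 | 81.5% |
| 10 / 38 | 80.4% |
| 10 / 35 | 80.3% |
| 10 / 34 | 79.1% |
| 9 / 43 | 78.0% |
| 9 / 39 | 77.5% |
| 8 / 34 | 71.3% |

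Losing up to eight benign labels costs about one point (81.5 − 80.3 = 1.2). The apparent step between 10/35 and 10/34 comes from the discreteness of the exact test: the uncorrected normal approximation gives about 80% at 10/34. The protocol does not say which form is used, so 10/35 is not a threshold of the plan. The last two rows correspond to about 10% and 20% of patients unlabelled. Those rates are assumed, since the documents give none.

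**4. Separating case mix from eligibility wording**

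Assume each patient is malignant independently with probability 10/53 = 0.189. The cancer count is then Binomial(N, 10/53), and power is averaged over it.

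| Labelled patients N | P(9 or fewer cancers) | Average power |
|---|---|---|
| 53 | 44.5% | 79.2% |
| 52 | 47.1% | 78.3% |
| 51 | 49.8% | 77.4% |
| 50 | 52.5% | 76.5% |

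The first fall, 81.5 − 79.2 = 2.3 points, arises with all 53 patients labelled, so it has nothing to do with the eligibility text. The later falls average (79.2 − 76.5) / 3 = 0.9 point per place. They occur only if unlabelled patients are enrolled against 4.1 and 10.1, and only if they are not replaced.

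**The case for a change.** The best argument for a change is that the checklist is the working gate. It is headed as taken from the approved protocol, yet it omits a condition of the criterion it reproduces, and it is what the study team signs. Someone working from that page alone could enrol a patient whom 4.1 and 10.1 do not describe, and nothing later in the protocol says whether that patient would be replaced. Aligning the wording would need no new procedure or visit.

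Part of this stands. The two eligibility texts do differ, neither repeats the condition in 4.1 and 10.1, and the protocol is silent on replacement.

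The consequence does not follow. Section 10.7 words 53 as an expectation, and Section 10.4.1 applies the same number to an analysis population made up of cancer and non-cancer patients. Nothing forbids enrolling another patient when one has no label. Adding a planned-procedure condition would restate a population already described in two sections. If the condition on aspiration were kept as well, the text would still not match 4.1 and 10.1 for resection patients. Nor would it prevent non-diagnostic or indeterminate results, which can also leave a patient unlabelled. Annotating the power statement would qualify a figure that is already correct.

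**Conclusion.** No change to the plan follows. The difference between 3.1.2 and Appendix A item 2 is a clerical inconsistency, and the intended population is clear from 4.1, 10.1 and 3.2.2. A team following the whole protocol would scan patients on their way to aspiration or resection, and the analysts would compare those with a malignant or benign result.

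The stated 80% holds at about 81% for 10 versus 43. One lost cancer label gives about 78%. The average of about 79% reflects an uncertain cancer count under an assumed independent binomial model, not the eligibility wording. The loss of 0.9 point per unlabelled patient rests on a fixed ceiling of 53 and on enrolment outside 4.1 and 10.1; the documents support neither. The power figures assume Gaussian data with the protocol's difference and SD. The conclusion does not depend on how the availability qualifier in Section 9.1 is read.

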3.2. Exclusion Criteria

- 3.2.1.** Patients younger than 18
- 3.2.2.** Patients who are unable to lie supine for a biopsy.
- 3.2.3.** Pregnant patients

3.3. Informed Consent Process

All participants must be provided a consent form describing the study with sufficient information for participants to make an informed decision regarding their participation. Participants must sign the IRB approved informed consent prior to participation in any study specific procedure. The participant must receive a copy of the signed and dated consent

document. The original signed copy of the consent document must be retained in the medical record or research file.

3.4. Randomization Procedures

This is an open label study, therefore patients will not be randomized.

3.5. Study Timeline

3.5.1. Primary Completion:

The study will reach primary completion 36 months from the time the study opens to accrual.

3.6. Study Completion:

The study will reach study completion 36 months from the time the study opens to accrual.

4. IMAGING AGENT/DEVICE/PROCEDURE INFORMATION

4.1. Name of Study Agent/Device/Imaging Procedure

No imaging agent will be used in this study.

- The examination will consist of an ultrasound elastography assessment in which an ultrasound machine is used to evaluate elastography measurements of a thyroid nodule.
- Each patient will undergo one ultrasound elastography assessment of the thyroid prior to either fine needle aspiration or surgical resection of the thyroid nodule (invasive procedure is not part of the study)
- No radiation will be used for this examination. Ultrasound is an imaging modality that uses sound waves, not radiation in imaging.
- Ultrasound machines are FDA approved.

5. STUDY PROCEDURES

5.1 Criteria for Removal from Study

After patient has ultrasound elastography of the thyroid nodule, they will have completed the study. If the patient cannot lie still in supine position then they will be removed from the study.

5.2 Alternatives

Alternative is to not participate in the study and continue with planned standard of care ultrasound and/or fine needle aspiration of thyroid nodule.

6. STUDY CALENDAR

	Pre-Study	Procedure- post consent
Investigational Agent		

Informed consent	X	
Radiologic evaluation (ultrasound)		X

7. ADVERSE EVENTS AND REPORTING PROCEDURES

7.1. Potential Adverse Events

There are no known side effects or adverse events from elastography. However, if any are detected, they will be reported.

7.2. Adverse Event Reporting

No adverse events are expected to occur in this study.

Adverse events will be graded according to CTCAE v4.0. Both Serious and Non-Serious Adverse Events will be clearly noted in source documentation and listed on study specific Case Report Forms (CRFs). The Protocol Director (PD) or designee will assess each Adverse Event (AE) to determine whether it is unexpected according to the Informed Consent, Protocol Document, or Investigator's Brochures, and related to the investigation. All Serious Adverse Events (SAEs) will be tracked until resolution and 30 days after the last dose of the study treatment.

8. REGULATORY CONSIDERATIONS

8.1. Institutional Review of Protocol

The protocol, the proposed informed consent and all forms of participant information related to the study (e.g. advertisements used to recruit participants) will be reviewed and approved by the Stanford IRB and Scientific Review Committee (SRC). Any changes made to the protocol will be submitted as a modification and will be approved by the IRB and SRC prior to implementation. The Protocol Director will disseminate the protocol amendment information to all participating investigators.

8.2. Data Management Plan

Data will be stored in Oncore and REDCap. Other data will be stored on a password protected and encrypted computer or on a HIPAA compliant server through Stanford, BOX.

8.3. Data and Safety Monitoring Plan

During the clinical investigation, the Protocol Director will evaluate the progress of the trial, including periodic assessments of data quality and timeliness, participant recruitment, accrual and retention, participant risk versus benefit, and other factors that can affect study outcome.

The Stanford Cancer Institute Data and Safety Monitoring Committee (DSMC) will audit study related activities at least annually in accordance with the DSMC SOP to determine whether the study has been conducted in accordance with the protocol, local standard operating procedures, FDA regulations, and Good Clinical Practice (GCP). This may include review of regulatory binders, case report forms, eligibility checklists, and source documents. In addition, the DSMC will regularly review serious adverse events and protocol deviations associated with the research to ensure the protection of human subjects. Results of DSMC audits will be communicated to the IRB and the appropriate regulatory authorities at the time of continuing review, or in an expedited fashion, as needed.

9. MEASUREMENTS

9.1. Primary and Secondary Outcome measures

Elastography shear wave velocity measurements of thyroid nodules will be compared to fine needle aspiration biopsy results or surgical pathologic specimens, if available. No secondary outcome measurements will be made.

9.2. Measurement methods

Elastography shear wave velocity measurements of thyroid nodules (which are calculated by the ultrasound machine at the time of the elastography measurements) will be compared to fine needle aspiration biopsy results or surgical pathologic specimens, if applicable.

9.3. Measurement Time Points

Elastography shear wave velocity measurements of thyroid nodules will be compared to fine needle aspiration biopsy results or surgical pathologic specimens, if applicable. No follow-up imaging or assessment will be required.

9.4. Response Review

No response review is planned.

9.5. Secondary Outcome

There is no secondary outcome.

10. STATISTICAL CONSIDERATIONS

10.1. Statistical Design

This is a prospective single arm blinded study in which patients who come for biopsy or surgical resection will be analyzed with elastography prior to biopsy or surgical resection. A sample size of 10 vs 43 provide 80% power for detecting a difference of 0.84 m/sec at the significance level of 0.05 based on Wilcoxon rank sum test assuming that the sound velocity for benign (and malignant nodules) follows a Gaussian distribution). The standard deviation is 0.79 meters/second based on the observed standard deviation from our pilot data.

We propose to use Wilcoxon rank sum test for its robustness in cases where the velocity does not follow the Gaussian distribution. Even if the Gaussian assumption is true, the Wilcoxon rank sum test is almost as powerful as the parametric t-test.

Randomization

Patients are not randomized in this study.

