10.4.2. Analysis Plan

Appropriate summary statistics will be provided for the sound velocity by the malignancy status. two-sided two sample Wilcoxon rank sum test will be used to compare of tissue stiffness measured by the sound velocity between malignant and benign nodules

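### Does the 80% power claim need changing because the expected 10 malignant cases among 53 patients have no stated source and nothing secures them?

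*Combined protocol and SAP*

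**What the plan says.** Section 10.1 gives one power figure for one split: "A sample size of 10 vs 43 provide 80% power for detecting a difference of 0.84 m/sec at the significance level of 0.05". It assumes Gaussian velocities, an SD of 0.79 m/s from pilot data and the Wilcoxon rank sum test. Section 10.4 makes that test two-sided.

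Section 10.4.1 presents the split as a forecast: "Analysis population is 53 patients expected to consist of 10 cancer patients and 43 non-cancer patients". Sections 10.6 and 10.7 fix only the total, 53 patients over three years. Section 10.2 provides a three-monthly look at the data without a stopping rule, and 8.3 has the Protocol Director review accrual. Neither ties an action to the number of malignant cases.

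On the malignancy rate, 2.4 says that "a minority, between 1.5 – 10% of thyroid nodules, are malignant". Section 2.5 reports preliminary data for direction only: "Preliminary results show that the stiffness or elastography values of malignant nodules tend to be greater than benign thyroid nodules". On who is enrolled, 10.1 says that "patients who come for biopsy or surgical resection will be analyzed with elastography prior to biopsy or surgical resection".

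On reporting, 10.4.2 says: "Appropriate summary statistics will be provided for the sound velocity by the malignancy status". Section 10.3 specifies mean and SD by malignancy status, with quantiles if the data are far from Gaussian. No interval for the difference is named.

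**The concern.** With 10 against 43, the smaller group largely determines the precision of the comparison, and the plan neither controls nor justifies its size. The pilot is cited for the SD and for the direction of the effect, not for a malignant share. Set beside the upper figure of 10% in 2.4, the assumed 18.9% is nearly double. At 10%, 53 patients would yield about 5 malignant nodules rather than 10.

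This is the only planned hypothesis test. If few malignant cases accrued and the test were non-significant, a reader could take the result as a negative from a study with 80% power when the real figure was nearer 55%. Section 10.8 makes a larger study depend on promising results, so that misreading could affect the next decision.

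The unit also appears to shift: 10.4.1 counts patients, while 10.4.2 sets out to "compare of tissue stiffness measured by the sound velocity between malignant and benign nodules".

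**Working it through.** **Inputs.** Difference 0.84 m/s, SD 0.79 m/s, groups of 10 and 43, Gaussian velocities (10.1); two-sided rank sum test at 0.05 (10.4); total 53 (10.6). Equal SDs and one nodule per patient are assumed.

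**1. Reproducing the 80%.** The standardised difference is 0.84/0.79 = 1.063.

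- Noether's approximation: the probability that a malignant value exceeds a benign one is Φ(1.063/√2) = 0.774. Power = Φ(√(12 × 0.1887 × 0.8113 × 53) × 0.274 − 1.96) = Φ(0.743) = 77%.
- Noncentral t-test, noncentrality 1.063/√(1/10 + 1/43) = 3.03: 84%.
- Simulation with the exact rank-sum critical value: 81 to 82%.

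The stated 80% is reproduced.

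**2. Power by malignant count.** Same exact test, total held at 53:

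| Malignant | Benign | Power |
|---|---|---|
| 5 | 48 | 55% |
| 7 | 46 | 69% |
| 8 | 45 | 74% |
| 9 | 44 | 79% |
| 10 | 43 | 81 to 82% |
| 13 | 40 | 89% |

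This table needs a definite result for all 53. Section 9.1 uses pathology where available, so some may be missing. The loss is small: 10 vs 38 gives about 80%, and 8 vs 37 about 72%.

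**3. Spread of the count if the planned share is right.** For Binomial(53, 10/53):

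- fewer than 10: 44%; exactly 10: 14%; more than 10: 42%
- 7 or fewer (power below 70%): 19%
- 5 or fewer (power about 55% or less): 5%

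Average power is 71% given fewer than 10 and 86% given 10 or more. Overall: 0.445 × 0.706 + 0.555 × 0.860 = 0.314 + 0.477 = 0.79. The random count therefore costs about 2 points against the 81 to 82% at exactly 10, or 1 point against the stated 80%.

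**4. If the share is different.** Average power over the binomial count, with shares other than 18.9% taken as assumptions:

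| Share | Expected malignant | Chance of fewer than 10 | Average power |
|---|---|---|---|
| 10% | 5.3 | 96% | 55% |
| 15% | 8.0 | 73% | 71% |
| 18.9% | 10.0 | 44% | 79% |
| 25% | 13.3 | 11% | 87% |

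The 10% row applies only if the general figure in 2.4 held in enrolled patients. Section 2.4 itself describes referral of nodules for biopsy or excision, and the study enrols from that referred group. A higher share there is plausible, but the documents give no number.

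**5. The unit.** Inclusion criterion 3.1.2 refers to a single nodule, and 4.1 says: "Each patient will undergo one ultrasound elastography assessment of the thyroid prior to either fine needle aspiration or surgical resection of the thyroid nodule". Read as one nodule per patient, the counts of cancer patients and malignant nodules are the same.

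**6. What the report will show anyway.** Group sizes, means and SDs by malignancy status allow an approximate interval. With SD 0.79, the t-based half-width at 10 vs 43 is 2.008 × 0.79 × √(1/10 + 1/43) = 0.56 m/s. At 5 vs 48 it is 2.008 × 0.79 × √(1/5 + 1/48) = 0.75 m/s. The matching rank-based half-widths are 0.58 and 0.79 m/s. A reader can see the loss of precision from the planned summaries.

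**The case for a change.** The strongest case for a change is that the one power claim in the plan rests on an input with no source, that the only rate in the document points lower, and that repair would cost a few sentences. Counts from 5 to 13 move power from 55% to 89%, and the planned reviews set no action on the count. Saying that the split is only expected does not meet the point, because the stated power depends on that expectation.

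Much of this stands. The share is undocumented, nothing secures it, and a sentence giving its basis would be good practice. Three things limit its weight. First, the comparison with 2.4 sets a general nodule rate against a referred group, so it does not show that 18.9% is too high. Second, falling below an expected value nearly half the time is what an expectation implies, and the chance of exceeding it is almost the same. Third, the remedies on offer disclose power without raising it. A confidence interval for the difference would be a useful addition to the report, but it is separate from the power claim. A rule against citing 80% power whenever fewer than 10 malignant cases accrue would also catch 9 cases, where power is 79%.

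**Conclusion.** No change to the plan follows. The 80% is correct for 10 vs 43 (exact power 81 to 82%), the plan labels that split as expected, and if the share is right the varying count leaves average power at about 79%. What remains is a missing source for one planning assumption. If the true share were lower, power would be lower, at about 71% for an assumed 15% and about 55% for 10%, but the rank sum test would remain valid and nothing in its conduct or in enrolment would alter. Analysts fill this gap in the ordinary way, by reporting the observed malignant count and reading a non-significant result against it.

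The conclusion rests on one nodule per patient, a common SD of 0.79 m/s, Gaussian velocities and a definite result for nearly all 53 patients. Some missing results cost little: 10 vs 38 still gives about 80%.
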